2. INTRODUCTION

2.1. Background and Rationale

The rationale of this trial is to test the usefulness of gabapentin in reducing and resolving pain in children with developmental brain disorders, specifically those with severe neurological impairment (SNI). The trial is part of a larger program of research focused on the problem of ongoing, unexplained, and difficult-to-treat pain and irritability that many children with SNI, and their families, experience. Our program goal is to improve the assessment and treatment of pain and irritability in children with complex health conditions and multiple disabilities who have limited communication and cognition. These children are amongst the most vulnerable seen in any hospital or clinic.

Severe Neurological Impairment (SNI)

SNI is an overarching descriptive term for children with significant health and functional challenges due to disorders affecting the neurological system, both acquired and congenital. In SNI, cognition and communication are affected and often motor skills, vision, hearing, and autonomic function (temperature, digestion, etc.) are also impaired. SNI is a result of diverse conditions, such as hypoxic-ischemic encephalopathies (severe cerebral palsy), traumatic brain injuries, childhood neurodegenerative diseases, and many other genetic conditions.

Defining Pain in a Complex Pediatric Population

In a study of the prevalence of pain in the general pediatric population, 12% of children report some pain each week.¹ In several studies of children with SNI, however, pain is far more prevalent, and is seen in up to 42% of children on a daily basis.^{2–4} In one study, pain was a problem for 73% of children with SNI at least one day of every fourteen, and for 67% of these children the pain was rated moderate to severe by parents. As shown in our work and that of others, of all of the symptoms causing suffering, pain is the most common one reported by parents of children with SNI.^{5–9} Furthermore, the greater the degree of neurological impairment, the higher the prevalence of pain.¹⁰

The International Association for the Study of Pain (IASP) defines pain as "an unpleasant sensory and emotional experience associated with actual or potential tissue damage". Most people are familiar with nociceptive-inflammatory pain, in which an injury triggers nociceptive nerve activity followed by an inflammatory response (for example, from an everyday event such as stubbing a toe). There are several other types of pain, including direct nerve injury (neuropathic pain) that activates nerve pathways without accompanying inflammation 12–14 and central or functional pain that arises entirely within the central nervous system, more recently termed 'nociplastic' pain. 5,16 Some authors also hold that visceral pain from internal organs is itself a distinct category involving a specific physiology, but this is not always clear. 17,18

Pain is the most common symptom reported by the parents and caregivers of children with SNI, ¹⁹ however, pain is notoriously difficult to identify, and therefore treat, in non-verbal children because their signals of distress are ambiguous and hard to decode. Typical distress behaviours include crying, tears, facial grimace, limb withdrawal, arching, hypertonicity, and decreased sleep.

More mobile children may curl up into a ball, fling their arms or legs, or engage in self-injurious behaviour; they may even display decreased activity. 20-25

Children with SNI may experience nociceptive-inflammatory pain as a result of their specific medical condition (e.g. joint contractures) or from many procedures that they experience (e.g. injections). Often, however, it is not clear what underlies the pain behavior as there is no clear inciting noxious event; our team has defined this entity of pain without an obvious source as Pain and Irritability of Unknown Origin (PIUO). Of the pain without an obvious source as Pain and Irritability of Unknown Origin (PIUO).

Parents are experts in identifying pain behaviours in their own child, but consider their interpretation to be a complex and uncertain process.²⁹⁻³¹ As well, while pain behaviours can be described by clinicians and parents, the behaviours themselves are subjective, ambiguous, and can reflect a variety of problems in addition to pain.³² Unless one witnesses an obvious nociceptive-inflammatory trigger such as an injury, parents and clinicians find it very difficult to ascribe all of the pain-like behaviours observed in children with SNI to pain as defined by the IASP. In this context, the term "pain" does not serve as a descriptive label. Therefore, we describe pain behaviour episodes using a less deterministic term, "pain and irritability," acknowledging that the behaviour is certainly negative in the eyes of the witnessing caregiver.

Addressing Assessment and Management of PIUO

As clinicians who care for these children, our goal is to improve the assessment and treatment of PIUO; yet there is no consensus among care providers about how best to approach PIUO. Lacking an explanation for the source leaves clinicians unable to treat the pain and increases a parent's obstacles in providing care. 33,34 Much is known about the assessment and treatment of both acute and chronic pain in typically developing children, from neonates to adolescents. While the treatment for an individual patient might pose significant clinical challenges (e.g. treating cancer pain in a toddler), the outlines of what to search for, the likely sources, and the starting points for treatment are clear. Care of a young child in pain begins with emotional-physical care such as hugging and soothing. Analgesics such as acetaminophen are used first and pain management may progress to powerful agents such as fentanyl and ketamine. The sequence of interventions reflects knowledge of how the nervous system develops and responds to stimuli in the typical child. Children with SNI have marked differences in their nervous system because of differences in brain anatomy, injury to the developing brain, disruptions in healthy cell metabolism, or a host of other disruptions. Since clinicians cannot make the same assumptions and inferences about pain signals or responses as with the typical child, they need better tools to address pain in these children.

Our work to date has developed a more efficient, focused clinical pathway to evaluate children with SNI for all potential sources of nociceptive-inflammatory ("treatable") pain. We are currently conducting a multi-site randomized, controlled trial of this clinical pathway. Our objective is to reduce the "unknown" element of pain in these children, increasing the potential for treatment. Nevertheless, there are children, who at the end of a thorough evaluation guided by a clinical pathway, will still have PIUO. These children may benefit from adjuvant analgesics such as gabapentin.

Treating with Gabapentin

According to the US FDA product information (US FDA Neurontin (gabapentin) Prescribing Information. Revised: 10/2017. Available at: https://www.accessdata.fda.gov/drugsatfda_docs/la-bel/2017/020235s064_020882s047_021129s046lbl.pdf Accessed October 4, 2020), gabapentin is indicated for adjunctive therapy in the treatment of partial onset seizures, with and without secondary generalization, in adults and pediatric patients 3 years and older with epilepsy. In Canada, however, gabapentin is authorized for use in adults only (> 18 years of age) as an antiepileptic agent and is not indicated for use in children. The precise mechanisms by which gabapentin produces its analgesic and antiepileptic actions are unknown. Gabapentin is structurally related to the neurotransmitter gamma-aminobutyric acid (GABA) but has no effect on GABA binding, uptake, or degradation. Much is known about its activity at the molecular level and there is increasing understanding that it moderates nerve signals that include pain. Gabapentin is notable for not being metabolized in humans; the parent compound is renally excreted with an elimination t1/2 of 5-7 hours.

In studies of gabapentin the main adverse effects are development of sedation and dizziness, ataxia, fatigue, and nystagmus in people 12 and older. In children aged 3-7 treated for epilepsy there was also a small increase, compared to controls of weight gain, susceptibility to viral ill ness, somnolence and hostility. (US FDA Neurontin (gabapentin) Prescribing Information. Revised: 10/2017. Available at: https://www.accessdata.fda.gov/drugsatfda_docs/la-bel/2017/020235s064_020882s047_021129s046lbl.pdf Accessed October 4, 2020),

Gabapentin was originally developed as an anti-convulsant. In the first 10 years of its use attempts were made to find its place as a monotherapy, and later an add-on therapy, for seizures. Starting in 1996 and continuing onward there was an explosion of interest in this drug as an analgesic, especially for neuropathic and chronic, complex pain. Gabapentin is often used for these indications as it has a low adverse event profile and appears to provide clinical benefit in difficult-to-treat cases. Clinical use of gabapentin for these same indications of neuropathic and chronic pain, as well as pain and irritability, has extended to infants and children. In a longitudinal, prospective study of children with non-cancer life-threatening conditions, gabapentin was used by 13.8% of the subjects. On the subjects.

Gabapentin was tested in 118 pediatric patients age 3 to 12 years with epilepsy. This study showed that gabapentin was significantly better than placebo. The drug's pharmacokinetics were established in 48 pediatric subjects between the ages of 1 month and 12 years. The dosing was tested with 253 pediatric subjects between 1 month and 13 years of age. A smaller study in pediatric patients age 1 month to 3 years compared dosing of 40 mg/kg/day gabapentin (N=38) with placebo (N=38) in patients who were receiving at least one marketed antiepileptic drug and had at least one partial seizure during the screening period, and this study showed no difference between product and placebo (Scientific Information, Teva Canada Ltd. https://www.tevacan-ada.com/globalassets/canada-ph2/product-monographs/teva-gabapentine-capsules-100-300-400-tablets-600-800mg_pm.pdf, accessed June 1st, 2020 and Product Information, Pfizer Canada Inc. https://www.pfizer.ca/sites/default/files/202005/Neurontin_PM_E_237475_2020.05.05.pdf accessed on June 1st, 2020).

The evidence base supporting the use of gabapentin for pain and irritability in infants and children with neurological impairment rests on case series publications describing a limited number of retrospective cases. ⁴¹⁻⁴⁹ The lack of prospective, randomized studies, even for this commonly-used medication, underpins the rationale for this study.

The N-of-1 trial design chosen for this study is suitable for a small-scale study, the first randomized, placebo-controlled study in this population and for this indication (children with neurological impairment and potential neurological dysregulation). Results from this study are expected to be useful in the design of a much larger Randomized Clinical Trial (RCT) that will provide further information about the effectiveness, dosing and adverse effects of the medication.

2.2. Objectives

The primary objective of the trial is to evaluate the effectiveness of gabapentin to decrease pain and irritability in children with SNI, when the source of pain and irritability is attributed to neurological dysregulation (nociplastic pain), as measured by parent reported pain scores. This objective corresponds to the primary outcome listed in section 3.4.1.

We will compare the gabapentin versus placebo along an escalating dose range for both individual subjects and for the group. We will aggregate the results of the completed N-of-1 trials across all subjects to estimate the group level comparative effectiveness of gabapentin in reducing pain and irritability.

The secondary objectives are to:

- 1. Identify the optimal dosing of gabapentin in reducing pain and irritability (Corresponds to secondary outcomes 3.4.2 and 3.4.3).
- 2. Identify the latency time for gabapentin to show effectiveness (Corresponds to secondary outcome 3.4.4).
- 3. Evaluate the safety and tolerability of gabapentin (Corresponds to secondary outcome 3.4.5).
- 4. An Exploratory objective will be to evaluate whether parent/caregiver stress and function improve if gabapentin reduces children's pain and irritability. This objective corresponds to the Exploratory outcome listed in section 3.4.6.

2.3. Trial Design

With the small sample size and time needed to titrate up to an effective dose, this trial proposes to use a single randomized multiple-measures cross-over design (N-of-1), with results aggregated over several subjects. This design is well-suited to outcomes that are highly specific to each individual and not amenable to precise measurement across a large cohort. The heterogenous nature

of pain and irritability responses in children are more likely to be personally specific and characteristic, rather than generalizable. The behavioural pattern is reflected in the structure of the standard tools for pain assessment in SNI that rely upon a catalogue of behaviour patterns that differ from one child to the next.^{3,29,50-52}

The proposed cross-over trial will use randomization and blinding of subjects and observers with placebo controls to reduce unexpected bias. A critical distinction is that each subject will serve as their own control and experiment, allowing for a finer assessment of the treatment efficacy within each patient.

In this trial, each patient will switch between gabapentin (G) and placebo (P). The sequence of whether G precedes P (GP) or P precedes G (PG) will be randomized by the study pharmacist, and neither the clinician nor the subject (parent/caregiver) will know the sequence.

Gabapentin is clinically started at a low dose and increased until either effectiveness is demonstrated or an upper limit dose, derived empirically, is reached. Based on work by [name] and Solodiuk we have established a dose titration schedule that will reach a typically effective dose over 15 days ([name], personal communication).⁴⁴ Extensive expert opinion shows that in the setting of children with neurological irritability and pain, as opposed to functional chronic pain in other children/youth, the onset of pain relief is much more rapid than several weeks. Ref. 49 describes improvement in pain scores (NPASS) in a neonatal cohort at 14 days. In another study, an RCT of gabapentin in children, a stable dose was reached at 22 days, and clinical effect was seen within that time frame, even though the protocol continued to 30 days. [Effectiveness of Gabapentin on Chronic Irritability in Neurologically Impaired Children. ClinicalTrials.gov Identifier: NCT01675960. The trial was terminated due to slow recruitment (2 enrolled)]. In personal communication with the study PI, ([name]), most of the effect was actually within 2 weeks and this is confirmed in his clinical practice. [name], author of Ref 41, 43 and 44 concurs with this time frame, in personal communication. Parent-caregivers will administer either active gabapentin or placebo on the same schedule. When transitioning between gabapentin and placebo, in either direction, there will be a 3-day washout period. A study dosing table is shown in Section 3 3

The primary variable assessed is the child's pain score. Pain and irritability will be measured using the Non-Communicating Children's Pain Checklist – Revised (NCCPC-R) at specified intervals throughout the randomized sequence of G: P. Additional measures of parent/caregiver burden and impact on their daily function will be undertaken weekly with the PROMIS-57, a tool adapted to measure the impact of the child's pain and irritability on parental functioning. This multi-dimensional tool assesses the parent/caregiver's stress, activity, function and sleep and is a proxy for the distress caused by the child's condition.

Other measures will be of usual, known side effects (e.g., sedation) and of any unexpected adverse events. Known side effects will be assessed regularly at the start, mid-point and end of each sequence via the Health Update. Unexpected adverse events will be tracked continuously.

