Risk minimization, management, and assessment procedures have been implemented in the study to minimize and assess potential risks to participants who participate in this clinical study with gabapentin. Components include: (1) specific study eligibility and exclusion criteria to ensure that participants who have underlying characteristics that potentially increase their risk for an adverse outcome are excluded. These include patients with a history of previous sensitivity to gabapentin. (2) Protocol-specific procedures for minimizing and managing AEs: sedation is the most common AE to gabapentin, and we will address this by titrating upwards on the dose every 3rd day, and always increasing the nighttime dose first; (3) overview surveillance by the independent Data Safety Monitoring Board; (4) ongoing follow-up throughout the study by research personnel twice weekly, coinciding with dose increases to check for AE as shown in the table below.

Refer to the TEVA-Gabapentin (gabapentin) TEVA Canada Product Monograph (DIN 02244515) for a detailed description of warnings, precautions, and adverse events: https://health-products.canada.ca/dpd-bdpp/info.do?lang=en&code=68492

The following potential side effects occurred in clinical trials across ages 3-adults at rates higher than in placebo groups:

- Somnolence
- Dizziness
- Fatigue
- Nausea and/or Vomiting
- Increase Weight
- Emotional Lability
- Hostility
- Hyperkinesia
- Respiratory Infection
- Fever
- Swelling of limbs
- Gait disturbance

Implementation and adherence

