The risk of serious side effects of respiratory depression with concomitant use with opioids is acknowledged (BC Children's Hospital Integrated Pain Service Gabapentin Information http://www.bcchildrens.ca/Pain-Services-Site/Docu-Sheet. Accessed at: ments/BCCH1455Gabapentin.pdf. Retrieved on October 4, 2020). A minority of patients might be on opioids. Dose adjustments will be added when gabapentin is used with a concomitant opioid or other CNS depressant medication: the family will be advised to return to the previous stable, safe dose in the protocol, and the subject will remain at that dose with no further escalation for the duration of the trial arm. This schedule will be duplicated on the parallel arm (active drug or placebo) to maintain masking. The participants are highly monitored, often with continuous oxygen saturation monitoring and/or "baby-cam" devices observing them during sleep. During the daytime they are with family, or professional caregivers (aides, nurses, etc.). These individuals will be advised to watch for respiratory depression and sedation that occur well before fatal apnea, and how to respond.

While there are no prohibitions on concomitant care, any care or medications unrelated to the trial will be noted in the CRFs for each participant.

Participants are sometimes obtaining respite care at facilities with nursing and physician care. Medical reconciliation is done at each admission. Parents will be provided with a letter to share with these programs outlining the study, the drug being tested, and a 24-hour pager to contact for further information or concerns

Active Participants < 15kg in mg per kg

Day	Morning mg/kg	Noon mg/kg	Evening mg/kg	Total mg/kg per day	% Change
1*	0	0	5	5	0
2	0	5	5	10	100%
3	5	5	5	15	50%
4	5	5	5	15	0%
5	5	5	10	20	33%
6	5	5	10	20	0%
7	5	5	10	20	0%
8	10	10	10	30	50%
9	10	10	10	30	0%
10	10	10	10	30	0%
11	13.3	13.3	13.3	40	33%
12	13.3	13.3	13.3	40	0%
13	13.3	13.3	13.3	40	0%
14	17	17	17	50	25%
15	17	17	17	50	0%
16	17	17	17	50	0%
17	20	20	20	60	20%
18	20	20	20	60	0%
19	20	20	20	60	0%
20	13.3	13.3	13.3	40	-33%
21	6.7	6.7	6.7	20	-50%
22	0	5	5	10	-50%
23	0	0	5	5	-50%
24	0	0	0	0	-100%
25	0	0	0	0	0%
Switch over*	-	-	-	-	-

^{*}Day one or 26 if switching over, not both.

Active Participants > = 15kg in mg per day

Day	Morning mg	Noon mg	Evening mg	Total mg/kg per day	Total mg/day	% Change
1*	0	0	75	5	75	0
2	0	75	75	10	150	100%
3	75	75	75	15	225	50%
4	75	75	75	15	225	0%
5	100	100	100	20	300	33%

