Randomization will be undertaken by the study pharmacist, using a computer-generated randomization. Before the 2 periods (pair of active drug (G) or placebo (P)) the pharmacist will generate a random code indicating whether G or P is to be given first. The randomization table will be kept in the Research Pharmacy office, which has restricted access. In case of a serious adverse event and when necessary, the randomization of any one participant can be unmasked to the Principal Investigator. This will be done through direct contact between the pharmacist and the Principal Investigator.

Study Contacts

Contact with study participants during the trial will consist of online surveys and telephone check ins. Contacts will be scheduled to overlap with changes in dose. Each contact will last approximately 10 minutes. The following study tools will be used at study contacts (see table 4 for a schedule of assessments at the time of study contacts):

- Health Update (Appendix 6) (midway through each sequence and at study end)
- Pain Survey (Appendix) (only on the first or last day of each block, not both)
- NCCPC-R (Appendix 7)
- PROMIS-57 (Appendix 8)
- Adverse Events Log (Appendix 10)
- Concomitant Medications (Appendix 11)

When the participant begins Sequence 2, the drug will be dispensed again in person.

Follow up

Two weeks past Study End the randomization sequence for individual participants will be unblinded and shared with the participants along with their individual results. The results will be presented numerically and graphically. Graphs showing the outcomes over time on the medication and placebo arms, summarizing the dosage used at individual outcome points will be provided. This will allow participants to make decisions regarding continuing gabapentin (in consultation with their primary caregiver) and is in keeping the Strategies for Patient Oriented Research (SPOR) principles that this clinical care trial is based on. At this time, the participant's caregiver will also be given the opportunity to provide feedback to the research team via the Participation Questionnaire (Appendix 9).

For any participant that experiences a SAE, there will be an initial contact at the time of the event and appropriate evaluation undertaken by the physician investigator. Another safety follow-up visit will be scheduled within 7 days following the final study visit to review the event. Additional follow-up may be done based on the investigator's medical judgment.

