3.12. Safety/Harms

The safety analyses will include all data with no exclusions allowed because of protocol deviations.

Definition of Adverse Events

An AE is any untoward medical occurrence in a patient or clinical investigation participant, administered a study medication/intervention, which does not necessarily have a causal relationship with this treatment. An AE can therefore be any unfavorable and unintended sign (including an abnormal laboratory finding), symptom, or disease temporally associated with the use of a medicinal (investigational) study medication/intervention, whether or not related to the medicinal (investigational) study medication/intervention.

During each contact with the participant and the participant's caregiver, information on AEs will be gathered and documented accordingly. AEs will be graded as mild, moderate, severe or life threatening and assessed by causality as probably related, possibly related, unlikely to be related or not related to the study drug.

Other clinically significant AEs are those that cause the study participant discomfort or interfere with normal functions such as feeding, sleep, activity, etc. In this study these are likely to be the new onset of known side effects of gabapentin, as listed in the Health Update, or any other events that the parent-caregiver is concerned about.

Definition of Serious Adverse Events

An SAE is defined as an AE meeting one of the following criteria at any dose:

• Results in death during the period of protocol-defined surveillance

- Is a life-threatening event (defined as a participant at immediate risk of death at the time of the event)
- Results in in-patient hospitalization or prolongation of existing hospitalization during the period of protocol-defined surveillance
- Results in persistent or significant disability or incapacity. (Disability is defined as a substantial disruption of a person's ability to conduct normal life functions)

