^{*}If the child participated in the PIUO Study within the last 6 months these items will already be completed and only a Health Update is necessary to complete prior to drug dispensing. If the child did not participate in the PIUO Study all items will be completed and the PIUO Pathway will be implemented prior to drug dispensing. If a treatable cause for the child's PIUO is uncovered, the child will be withdrawn from the gabapentin trial.

Version 3.0 October 4, 2020 Page 39 of 45

 Table 4: Medication and Placebo Assessment Schedule for all subjects

Day	Health Update	Concomitant Medications	NCCPC-R	Pain Survey	PROMIS-57
1	X	X	X	X	X
2					
3					
4					
5			X	X	
6					
7					
8			X		
9					
10					
11	X		X		
12			X	X	X
13			X		
14			X		
15			X		
16			X	X	X
17			X		
18			X		

Version 3.0 October 4, 2020 Page 40 of 45

19			X	X	X
20					
21					
22			X		
23					
24					
25					
Switch Over*	X	X	X	X	X

^{*}Day 1 or 26 if switching over, not both

Version 3.0 October 4, 2020 Page 41 of 45

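### The Health Update, the checklist for known side effects, falls on days 1, 11 and 26 only, so none is given on the days with the highest scheduled doses

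*Protocol*

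**What the plan says.** Section 2.3 divides safety collection in two. Known side effects, with sedation as the example, go to a structured form: "Known side effects will be assessed regularly at the start, mid-point and end of each sequence via the Health Update". Unexpected events are tracked continuously.

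Table 4 in section 6.2, titled "Medication and Placebo Assessment Schedule for all subjects", fixes the days. It marks the Health Update on day 1, day 11 and the switch-over row, whose footnote reads "Day 1 or 26 if switching over, not both".

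Section 3.8 words the timing differently: "Health Update (Appendix 6) (midway through each sequence and at study end".

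Section 3.3 also promises "ongoing follow-up throughout the study by research personnel twice weekly, coinciding with dose increases to check for AE as shown in the table below". Section 3.12 requires active enquiry about adverse events at each contact. Of the clinically significant events expected, it says: "In this study these are likely to be the new onset of known side effects of gabapentin, as listed in the Health Update".

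The safety outcome in section 3.4 is defined on collected adverse events set against the Product Monograph. Section 3.10 compares adverse events between arms descriptively.

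**The concern.** The form that lists the expected effects is given once at a substantial active dose, on the first day of that dose step. It is not given again until after the wean. The highest scheduled doses lie in between.

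Two things depend on this. First, safety and tolerability is a secondary objective, and section 6.2 presents the design as able to show each child's tolerability. If dose-related effects were missed at the top of the titration, the safety outcome, which asks that events not exceed the monograph frequency, would be easier to meet. Second, the primary outcome is a score of observed behaviour on days 11-19. Section 3.3 calls sedation the most common adverse effect. Without structured sedation data on most of those days, a lower score is harder to interpret.

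**Working it through.** The plan gives no figure of its own to reproduce. The check sets Table 4 against the two active dosing tables in section 3.3.

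**Step 1. Scheduled dose on each Health Update day.** Share = dose that day / maximum dose in the same table. For children under 15 kg the day-11 row reads "11 13.3 13.3 13.3 40 33" (total 40 mg/kg/day, a 33% step up). The top step starts on day 17 with "17 20 20 20 60 20" (total 60 mg/kg/day).

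| Day | Under 15 kg (max 60 mg/kg/day) | 15 kg and over (max 675 mg/day) |
|---|---|---|
| 1 | 5; 5/60 = 8% | 75; 75/675 = 11% |
| 11 | 40; 40/60 = 67% | 600; 600/675 = 89% |
| 26 | 0 | 0 |

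Day 26 is taken as zero because both tables show zero on days 24 and 25 and give no dose in the switch-over row.

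**Step 2. Days above the day-11 dose.**
- Under 15 kg: days 14-16 at 50 and days 17-19 at 60 mg/kg/day, so 6 days. Health Updates on them: 0 of 6.
- 15 kg and over: days 14-17 at 675 mg/day, so 4 days (day 18 drops to 450). Health Updates on them: 0 of 4.

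**Step 3. Primary window.** Days 11-19 are 19 - 11 + 1 = 9 days. One has a Health Update (day 11) and eight do not.

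**Step 4. The end-of-period form.** The last top-dose day is day 19 (under 15 kg) or day 17 (15 kg and over). The gap to day 26 is 26 - 19 = 7 days or 26 - 17 = 9 days. Even if the form asks about the whole time since day 11, one answer would cover several dose steps and the wean.

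**Step 5. Other routes on days 12-19.**
- Section 3.12 questioning applies at each contact, but section 3.8 allows contacts to be online surveys as well as telephone calls. NCCPC-R is scheduled on every day from 11 to 19, yet an NCCPC-R day need not involve staff asking questions.
- The twice-weekly checks in section 3.3 refer to a table below. The tables that follow there give doses only.
- Section 3.8 refers to Table 4 for the timing of the contact tools, including the Adverse Events Log, but Table 4 has no adverse-event column. Table 3 marks the log by phase, without days.

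**Step 6. Consistency of timing.** Section 2.3 gives start, middle and end of each sequence. Section 3.8 omits the start of each sequence and the end of the first. Following the word mid-point literally would not help: (1 + 25)/2 = 13, still before the step on day 14.

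**The case against.** The strongest reply is that the Health Update is not the only safety instrument. Adverse events are to be asked about at every contact, research staff are to check twice weekly around dose increases, and new onset of an effect listed on the form itself counts as a clinically significant event. The safety outcome and the arm comparison use all collected adverse events, not this form. All of that stands, and it rules out several stronger conclusions that a reader might draw:

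- **That the safety comparison is biased toward no difference.** This would need the Health Update to be the sole source of side-effect data, which the documents contradict. They also give no event rates from which to compute a loss.
- **That effects at high dose are left to volunteered report.** Active questioning is required.
- **That these effects are never checked with the form at a child's highest dose.** Section 3.3 holds a child who benefits at the dose that worked, so day 11 may already be that child's own top dose. For children of 15 kg and over it is 89% of the maximum. The form itself is not in the text. If it asks about the time since the previous update, the day-26 form would reach back over the high-dose days.
- **That a fall in NCCPC-R cannot be told from sedation.** Day 11 lies in the window and has a form, and adverse-event questioning applies at contacts. Harder to separate is as far as the documents go.

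What the reply does not answer is that the structured list has no scheduled use at the highest scheduled doses, that the day grid does not show when the general checks occur, and that the timing statements differ.

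**Conclusion.** The point holds as a gap in structured collection, not as a demonstrated bias. By schedule, the checklist for known side effects is given on 0 of 6 days (under 15 kg) and 0 of 4 days (15 kg and over) above the day-11 dose, and on 1 of 9 primary-window days. This carries a risk of under-detection at the top of the titration and weakens the reading of the primary score. The size of either effect cannot be stated from the documents.

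The counts assume that a child follows the full schedule in the dosing tables. They are less telling for a child held earlier at an effective dose. How much the gap matters also depends on the recall period in Appendix 6, which is unknown. The conflict in timing between sections 2.3 and 3.8, and the absence of the section 3.3 checks from Table 4, do not depend on these assumptions.

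**What to change.** - In Table 4, add the Health Update on days 16 and 19 of both periods, where NCCPC-R, Pain Survey and PROMIS-57 are already collected. Day 16 is a top-dose day in the table for 15 kg and over (675 mg/day). Day 19 is one for under 15 kg (60 mg/kg/day). Day 19 is already in the wean for the heavier group, which is why both days are needed.
- Keep days 1, 11 and 26. Forms within the primary window rise from 1 to 3 of 9 days. Coverage of days above the day-11 dose becomes 2 of 6 (under 15 kg) and 1 of 4 (15 kg and over).
- Keep all forms and all adverse events in the arm comparison, so that early titration and the wean still count. Report the day 11-19 forms additionally.
- Add the adverse-event checks to Table 4, and bring sections 2.3, 3.3 and 3.8 into line with it on timing.

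The cost is one table edit, some text alignment and two more short checklists per period for parents: 2 x 2 = 4 per child, or 40 forms over 10 children, at assessments that already take place.
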